
**1.0 STS Factors (continued)**

Factor	Definition
Status of the procedure	
Elective: The patient's cardiac function has been stable in the days or weeks prior to the operation. The procedure could be deferred without increased risk of compromised cardiac outcome.
 
Urgent: Procedure required during same hospitalization in order to minimize chance of further clinical deterioration. Examples include but are not limited to: Worsening, sudden chest pain, CHF, acute myocardial infarction (AMI), anatomy, IABP, unstable angina (USA) with intravenous (IV) nitroglycerin (NTG) or rest angina.
 
Emergent: Patients requiring emergency operations will have ongoing, refractory (difficult, complicated, and/or unmanageable) unrelenting cardiac compromise, with or without hemodynamic instability, and not responsive to any form of therapy except cardiac surgery. An emergency procedure is one in which there should be no delay in providing operative intervention. The patient's clinical status includes any of the following:
 
a. Ischemic dysfunction (any of the following):
 
(1) Ongoing ischemia including rest angina despite maximal medical therapy (medical and/or IABP));
 
(2) Acute Evolving Myocardial Infarction within 24 hours before surgery; or
 
(3) pulmonary edema requiring intubation.
 
b. Mechanical dysfunction (either of the following):
 
(1) shock with circulatory support; or
 
(2) shock without circulatory support.
 
Emergent Salvage: The patient is undergoing CPR en route to the OR or prior to anesthesia induction or has ongoing ECMO to maintain life.

[figure not shown]
## 2.0 Other Factors not Captured by Traditional Risk Score [54]

Co-morbidity	Definition/Criteria
Porcelain aorta or severely atherosclerotic aorta	Heavy circumferential calcification or severe atheromatous plaques of the entire ascending aorta extending to the arch such that aortic cross-clamping is not feasible.
Frailty	Slowness, weakness, exhaustion, wasting and malnutrition, poor endurance and inactivity, loss of independence Criteria: 
 
• 5-meter walking time
 
• Grip strength
 
• BMI <20 kg/m^2 and/or weight loss 5 kg/yr
 
• Serum albumin <3.5 g/dL
 
• Cognitive impairment or dementia
 

Sever liver disease/cirrhosis	Any of the following: 
 
• Child-Pugh class C
 
• MELD score ≥10
 
• Portal-caval, spleno-renal, or transjugular intrahepatic portal shunt
 
• Biopsy proven cirrhosis with portal hypertension or hepatocellular dysfunction
 

Hostile chest	Any of the following or other reasons that make redo operation through sternotomy or right anterior thoracotomy prohibitively hazardous: 
 
• Abnormal chest wall anatomy due to severe kyphoscoliosis or other skeletal abnormalities (including thoracoplasty, Potts' disease)
 
• Complications from prior surgery
 
• Evidence of severe radiation damage (eg, skin burns, bone destruction, muscle loss, lung fibrosis or esophageal stricture)
 
• History of multiple recurrent pleural effusions causing internal adhesions
 

IMA or other critical conduit(s) crossing midline and/or adherent to posterior table of sternum	A patent IMA graft that is adherent to the sternum such that injuring it during re-operation is likely. A patient may be considered extreme risk if any of the following are present: 
 
• The conduit(s) are radiographically indistinguishable from the posterior table of the sternum.
 
• The conduit(s) are radiographically distinguishable from the posterior table of the sternum but lie within 2-3 mm of the posterior table.
 

Severe pulmonary hypertension Severe right ventricular dysfunction	Primary or secondary pulmonary hypertension with PA systolic pressures greater than 2/3 of systemic pressure Criteria as defined by the guidelines (eg, TAPSE <15mm, RV end-systolic area >20 cm  )

## **APPENDIX IV: RESHEATH AND RECAPTURE DEFINITIONS**

The following definitions are applicable to the data elements on the Implant eCRF that address the use of the resheath and recapture feature.

Resheath attempt	An attempt to intentionally resheath only a portion of the TAV (including the frame) into the capsule of the delivery catheter (eg, with the intent to reposition of the valve during deployment).
Recapture attempt	An attempt to intentionally fully resheath the entire TAV (including the frame) into the capsule of the delivery catheter until there is no gap between capsule and the tip (eg, with the intent to enable re-crossing of the aortic valve or retrieval of the system, Panel D below).
Reposition	Repositioning of the TAV proximally or distally before final deployment
Retrieve	Retrieval of a partially deployed TAV

**Figure 17. (A)** Between 0 and 1/3 of the valve length outside of the capsule **(B)** between 1/3 and 2/3 of the valve length outside of the capsule **(C)** Point of no return: capsule marker in alignment with the spindle marker **(D)** Full recapture: entire valve resheathed into the capsule until there is no gap between capsule and the tip.

## **APPENDIX V: DEFINITIONS: SAFETY ENDPOINTS AND EFFICACY EVENTS**

Definitions of adverse events to be evaluated as clinical safety endpoints, other related complications, and efficacy events are provided in Sections 1.0, 2.0, and 3.0, respectively [54]. The CEC and site investigators will code safety endpoint events according to these definitions, using the associated code list provided on Section 4.0, Event Code List.

### **1.0 Safety Endpoint Definitions**

Mortality	
Cardiovascular mortality	Any of the following criteria: 
 
1) Death due to proximate cardiac cause (eg, myocardial infarction, cardiac tamponade, worsening heart failure)
 
2) Death caused by non-coronary vascular conditions such as neurological events, pulmonary embolism, ruptured aortic aneurysm, dissecting aneurysm, or other vascular disease
 
3) All procedure-related deaths, including those related to a complication of the procedure or treatment for a complication of the procedure
 
4) All valve-related deaths including structural or nonstructural valve dysfunction or other valve-related adverse events
 
5) Sudden or unwitnessed death
 
6) Death of unknown cause
 

Non-cardiovascular mortality	Any death in which the primary cause of death is clearly related to another condition (eg, trauma, cancer, suicide).

**1.0 Safety Endpoints (continued)**

Stroke and TIA

Diagnostic criteria
 
1) Acute episode of a focal or global neurological deficit with at least 1 of the following:
 
 
• change in the level of consciousness
 
• hemiplegia, hemiparesis
 
• numbness or sensory loss affecting 1 side of the body
 
• dysphasia or aphasia
 
• hemianopia
 
• amaurosis fugax
 
• other neurological signs or symptoms consistent with stroke
 
 
Stroke: duration of a focal or global neurological deficit <math>\geq 24</math> h; OR <math>< 24</math> h if available neuroimaging documents a new hemorrhage or infarct; OR the neurological deficit results in death
 
TIA: duration of a focal or global neurological deficit <math>< 24</math> h, any variable neuroimaging does not demonstrate a new hemorrhage or infarct
 
2) No other readily identifiable non-stroke cause for the clinical presentation (eg, brain tumor, trauma, infection, hypoglycemia, peripheral lesion, pharmacological influences), to be determined by or in conjunction with the neurologist
 
3) Confirmation of the diagnosis by at least 1 of the following:
 
 
• Neurologist or neurosurgical specialist
 
• Neuroimaging procedure (CT scan or brain MRI), but stroke may be diagnosed on clinical grounds alone
 

Stroke Definitions
 
Disabling stroke: an mRS score of 2 or more at 90 days and an increase in at least 1 mRS category from an individual’s pre-stroke baseline
 
Non-disabling stroke: an mRS score of <math>< 2</math> at 90 days or one that does not result in an increase in at least 1 mRS category from an individual’s pre-stroke baseline

Stroke Classifications
 
Ischemic: an acute episode of focal cerebral, spinal, or retinal dysfunction caused by infarction of the central nervous system tissue
 
Hemorrhagic: an acute episode of focal or global cerebral or spinal dysfunction caused by intraparenchymal, intraventricular, or subarachnoid hemorrhage
 
Undetermined: insufficient information to allow categorization as ischemic or hemorrhagic

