## 12. Statistical Design and Methods

### 12.1. Sample Size and Results Reporting

This study will involve 150 subjects with an attempted implant with the Medtronic TAVR system. The primary analysis will be performed when 150 consecutive subjects with an attempted implant have had the chance to complete 30-day follow-up. Results from the primary analysis will be used for regulatory submissions. Another analysis may be performed when all 150 subjects with an attempted implant have completed 1 year follow-up. The final analysis will be performed with all implanted subjects have completed 10-year follow-up.

This is not a hypothesis-driven study, therefore the sample size of 150 for the analysis was not determined by statistical sample size methods. However, a sample size of 150 subjects is adequate for a descriptive assessment of the procedural safety and efficacy of the Medtronic TAVR system in subjects with bicuspid aortic valves. The results from the primary endpoints of the Low Risk bicuspid study cohort will be compared to the procedural safety and efficacy results from the TAVR arm of the Low Risk Trial randomized cohort.

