LVEF	Left ventricular ejection fraction
LVOT	Left ventricular outflow tract
MI	Myocardial infarction
MR	Mitral Regurgitation
NYHA	New York Heart Association
PCI	Percutaneous coronary intervention
PPI	Permanent Pacemaker
PVL	Paravalvular Leak
QoL	Quality of Life
STS	Society of Thoracic Surgeons
TAVI	Transcatheter aortic valve implantation
TAVR	Transcatheter aortic valve replacement
TEE	Transesophageal echocardiography
TIA	Transient ischemic attack
TTE	Transthoracic echocardiography
UADE	Unanticipated Adverse Device Effect

3. Introduction

This Statistical Analysis Plan has been designed to document, before data are analyzed, the rationale for the study design, and the planned analyses that will be included in study reports. This statistical analysis plan is developed based on the Clinical Investigational Plan (CIP).

The purpose of this study is to evaluate procedural safety and efficacy of the Medtronic Transcatheter Aortic Valve Replacement system (Evolut PRO and Evolut R systems) in patients with severe bicuspid aortic valve stenosis who are at low predicted risk of mortality at 30 days with SAVR.

Data from this study will be used to support regulatory submissions related to the use of Medtronic TAVR for bicuspid aortic valve anatomy patients with severe aortic stenosis who are at a low predicated risk of mortality with SAVR.

A study report will be prepared for submission to FDA at the time when all 150 consecutive subjects with an attempted implant have had the chance to complete their 30-day follow-up visit, have died, or have exited from the study, for the purpose of seeking market approval. Another study report may be prepared at the time when all the 150 attempted implant subjects have completed their 1 year follow-up visit. After all subjects have completed all protocol-specified follow-up, a final clinical report including updated long-term safety and efficacy data will be prepared and submitted.

The results from the primary endpoints of the Low Risk bicuspid study cohort may be presented relative to the procedural safety and efficacy results from the TAVR arm of the Low Risk Trial randomized cohort.

4. Study Objectives

The primary objective is to assess procedural safety and efficacy of the Medtronic TAVR system in patients with severe bicuspid aortic valve stenosis who are at low predicted risk of mortality at 30 days with SAVR.

5. Investigation Plan

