7.2. General Methodology

Descriptive statistics will be used to report study data. For continuous variables (eg. age), the mean, median, standard deviation, minimum, maximum and interquartile ranges (IQR) will be presented. For categorical variables, the number and percentage of subjects in the category of interest will be presented.

For time to event variables, Kaplan-Meier analyses of event rates at 30 days, 1 year and annually through end of study will be presented. For these analyses, the time points will correspond to 30 days, 365 days, 730 days, 1095 days, 1460 days, 1825 days, 2190 days, 2555 days, 2920 days, 3285 days and 3650 days post implantation respectively. At each time point with data, the product limit estimate of the event, the number of subjects at risk, the number of subjects with events, and the 95% confidence interval will be presented. For subjects without an event, the date of censoring will be the latest date of all follow-up visits, assessments, and events (including death).

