7.4. Handling of Missing, Unused, and Spurious Data and Dropouts

Every effort will be undertaken to minimize missing data. In time-to-event outcomes drop-outs will be censored at the time of discontinuation, consistent with the Kaplan-Meier approach.

Missing (accidentally, due to withdrawal, missing follow-up or loss to follow-up, etc.), unused and spurious data will remain identifiable in the database. Data from subjects that cannot be analyzed for a specific variable will be displayed as missing in the relevant summary tables. In this manner, all data for a specific variable are accounted for. Unless otherwise specified, no statistical techniques will be used to impute missing data. The number of subjects included in each analysis will be reported so that the reader can assess the potential impact of missing data.

In the case of partial dates, if only the month and year are known, the event or assessment will be analyzed as if it occurred on the 15th of that month. If only the year is known, the event or assessment will be analyzed as if it occurred on June 30th of that year. These resolutions of partial dates are subject to the restrictions that events must occur no earlier than the procedure date.

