7.9. Evaluation of Objectives

7.9.1. Primary Safety Endpoint

All-cause Mortality or Disabling Stroke Rate at 30 days.

Hypothesis/Decision criteria:

No specific hypotheses or pass/fail criteria have been set. The analysis will be descriptive and no statistical hypothesis test will be performed.

Endpoint Definition/Parameters to Be Estimated:

The endpoint is the KM event rate of all-cause mortality or disabling stroke at 30 days post procedure.

Data Collection and Analysis Method:

Data will be collected on event case report form. Death and stroke events will be adjudicated by the CEC. CEC adjudicated all-cause mortality or disabling stroke will be used in the analysis.

Analysis Dataset:

This objective will be analyzed for all attempted implant set.

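### The primary analysis may run before the 90-day mRS that defines a disabling stroke, and neither document says how a stroke still unclassified at the cut is counted

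*Protocol*

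**What the plan says.** **Definition.** Protocol Appendix V (Safety Endpoints, Stroke Definitions) calls a stroke disabling when there is "an mRS score of 2 or more at 90 days and an increase in at least 1 mRS category" relative to the person's level before the stroke. A stroke is non-disabling if the mRS is below 2 at 90 days "or one that does not result in an increase in at least 1 mRS category". That second limb has no explicit 90-day tie. Protocol 8.1 (Other Evaluations) schedules the mRS 1 and 3 months after a stroke and gives no window.

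**Timing.** Protocol 12.1 states: "The primary analysis will be performed when 150 consecutive subjects with an attempted implant have had the chance to complete 30-day follow-up". SAP 6.2 says the same. SAP 3 sets the same milestone for the report to FDA and also accepts subjects who, in its words, "have died, or have exited from the study, for the purpose of seeking market approval". The 30-day visit window runs from day 30 to day 45 (Protocol 8.1). SAP 3 makes a 1-year report optional. After all follow-up is complete, "a final clinical report including updated long-term safety and efficacy data will be prepared and submitted".

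**Counting.** SAP 7.9.1: "CEC adjudicated all-cause mortality or disabling stroke will be used in the analysis". SAP 7.2: "For subjects without an event, the date of censoring will be the latest date of all follow-up visits, assessments, and events (including death". SAP 7.4: "Unless otherwise specified, no statistical techniques will be used to impute missing data".

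**The concern.** The endpoint has a 30-day window, but one of its two components can be determined only about 90 days after onset. The trigger looks at the first clock and ignores the second. A non-fatal stroke in one of the last subjects enrolled can therefore sit in the database at the cut without the score that the Protocol's own definition needs. Fatal strokes are not affected, because they count as deaths. Some strokes can arguably be classed early as non-disabling through the second limb of that definition. The gap is thus mainly about strokes whose mRS has risen, which are the ones that may prove disabling.

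At stake is the accuracy of the main safety figure in the report written to support approval. Protocol 12.1 also says this figure will be compared with the TAVR arm of the Low Risk Trial. No hypothesis or pass/fail rule is attached (SAP 7.9.1), so this concerns a descriptive estimate and not a test decision.

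**Working it through.** **1. The plan's own figure.** SAP Table 1 gives 4+13+1+2 = 20 events in 394+301+60+60 = 815 subjects, or 2.45% (stated as 2.4%). Then 150 × 20/815 = 3.68, rounded up to 4. The Clopper-Pearson interval for 4/150 is 0.73% to 6.69%, which matches the 0.7% to 6.7% in SAP Table 2. That table is not in error.

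**2. Calendar.** Let the stroke occur on day d (0 to 30). Its 90-day mRS falls on day d + 90, that is day 90 to 120. I take the 90 days from stroke onset, in line with the 3-month schedule in Protocol 8.1. Let the cut be C days after the last implant. A subject implanted x days before the last one is pending if x < 90 − C + d.

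Two values of C are used, and both are assumptions because no lock date is given. C = 45 is the first date on which every 30-day window has closed. C = 66 adds the 3-week eCRF target of Protocol 8.13.2. Accrual is assumed uniform over the estimated 12-24 months (365 to 730 days).

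| Cut | 90 − C + d | Subjects in the pending zone, of 150 | Chance per stroke, onset uniform over days 0-30 | Chance per stroke, onset at day 0 |
|---|---|---|---|---|
| Day 45 | 45 to 75 (mean 60) | 150×45/730 = 9.2 to 150×75/365 = 30.8 | 60/730 = 8.2% to 60/365 = 16.4% | 45/730 = 6.2% to 45/365 = 12.3% |
| Day 66 | 24 to 54 (mean 39) | 150×24/730 = 4.9 to 150×54/365 = 22.2 | 39/730 = 5.3% to 39/365 = 10.7% | 24/730 = 3.3% to 24/365 = 6.6% |

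The third column counts subjects, not strokes. The last column matters because Protocol 5.2 treats stroke as a procedural outcome, so early onset is plausible.

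**3. How a pending stroke is counted.** Under SAP 7.9.1 only a CEC-adjudicated disabling stroke is an event. Under SAP 7.2 everyone else is censored at the latest contact, and SAP 7.4 rules out imputation unless otherwise specified. A subject whose stroke has not been adjudicated disabling, with last contact after day 30, is therefore event-free at day 30. This is an inference from three rules; none of them mentions a pending stroke.

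**4. Effect of one such stroke.** With 4 true events in 150, the Kaplan-Meier rate is 2.67%. With one of them pending it is 3/150 = 2.00% (exact interval 0.41% to 5.73%). In a worked example with onset on day 2, censoring on that day instead gives 2.01%, so the choice of censoring date hardly matters.

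**5. Expected effect under the event-free reading.** The documents give no stroke rate, so take the extreme case in which all 4 planning events are non-fatal disabling strokes. The expected number pending runs from 4 × 39/730 = 0.21 to 4 × 60/365 = 0.66. Divided by 150, that is 0.14 to 0.44 percentage points. The planning events come from tricuspid studies with mean STS scores of 4.0 to 7.3, while this trial requires predicted mortality below 3%, so they are illustrative only.

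**The case against.** **Direction.** A reader might infer that the reported rate must be too low. The documents do not support that. Appendix V has both sites and the CEC code endpoint events from a list that holds only disabling and non-disabling stroke codes, with none for a stroke awaiting its score. Sites must report serious events within 72 hours (Protocol Table 7), so a site has to choose a code long before day 90. If the CEC also codes provisionally, a stroke coded disabling that later improves would make the rate too high. The CEC charter (Protocol 11.1) is not among the documents and may hold a rule. This objection stands: treatment as event-free is what the SAP rules imply, not something they state.

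**Timing.** A reader might also infer that the data will be cut at day 45. The trigger is a floor. Adjudication and independent validation (SAP 8) take time, and by about day 30 + 90 = 120 after the last implant every 90-day mark has passed. This stands too. But nothing in the plan requires that wait, and a later lock does not help for a subject who exits before the 90-day score.

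**Correction.** A third tempting inference is that, apart from the optional 1-year report, nothing can correct the figure until after year 10. Protocol 14.8 requires public posting within 1 year of the conclusion of the primary and secondary endpoints, and Protocol Table 9 requires progress reports to FDA at least annually. Both are earlier routes, although neither requires a recalculated rate.

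**Cost of a fallback.** Classifying from an earlier mRS departs from the 90-day definition. The rule used in the Low Risk Trial comparator is not in the documents. This is a fair warning, and any provisional classification should be labelled as a departure.

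**Conclusion.** The timing gap holds on the face of the text: the trigger permits a primary safety rate before its stroke component can be determined under the Protocol's own definition, and neither document says how an unclassified stroke is counted. The SAP rules imply that it is event-free, but a provisional CEC code could push the error either way.

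The effect is minor. Each non-fatal stroke by day 30 has about a 5-16% chance of being pending at a day-45 to day-66 cut, or about 3-12% if onset is at day 0. The expected shift is at most about 0.14-0.44 points, against a planning interval of 0.7% to 6.7%. One event misclassified as event-free moves 2.7% (0.7-6.7) to 2.0% (0.4-5.7). These figures rest on uniform accrual over 12-24 months, the assumed cut dates and, for the expected shift, all 4 planning events being non-fatal disabling strokes. It is still worth fixing, because the figure supports a submission and the remedy is cheap.

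**What to change.** 1. **Trigger (Protocol 12.1, SAP 3 and 6.2).** Run the primary analysis when all 150 subjects have had the chance to complete the 30-day visit and every subject with a stroke by day 30 has had the chance to complete the 3-month post-stroke mRS, within a stated window, or has died or exited. A missed score cannot stall the analysis, because the trigger depends on the window closing. Cost: a delay of up to 120 − 45 = 75 days from a day-45 cut, plus the mRS window, and only if a late stroke occurs.

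2. **Counting rule (SAP 7.9.1).** For any stroke with no 90-day mRS at the cut, for example after exit, report the number. State the CEC's provisional classification and its basis (the latest available post-stroke mRS), and label it as a departure from the 90-day definition. Add a sensitivity analysis that counts each such stroke as disabling and then each as non-disabling. SAP 7.4 leaves room for this. A basis will usually exist: the 1-month post-stroke mRS is outstanding only if x < 30 − C + d. At day 45 this averages (15²/2)/30 = 3.75 days over uniform onset, or 3.75/730 = 0.5% to 3.75/365 = 1.0% of strokes. At day 66 it is none. Cost: wording and one short table.

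3. **Secondary.** Protocol 8.5 limits safety follow-up to 30 days for subjects without a TAV and to 30 days after an explant, while Protocol 8.1 asks for an mRS 3 months after any stroke. Reconcile the two. The no-TAV group is negligible: SAP Table 1 has 808 implanted of 812, so 150 × 4/812 = 0.74 subjects would be expected.
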